4.1.3.11 Disease Control Rate (DCR)

Disease control rate (DCR) is defined as having a confirmed BOR of SD or better post-baseline during the Treatment Phase. The number and percentage of participants achieving disease control along with the 2-sided 95% Clopper-Pearson exact Cl for the DCR will be presented by age cohort. This will consider all subjects who have a baseline scan.

All tumor volume measurements will be independently calculated by two blinded reviewers. In the case that the two measurements represent different tumor response statuses, as defined in Section 4.1.1, an independent adjudicator will make the final decision on which response category is recorded at that visit.

As a sensitivity analysis, the DCR will also be summarized by each reader separately.

4.2 Safety Measures

The safety measures in this study include assessing treatment-emergent adverse events (TEAEs) (additionally by dose formulation), electrocardiograms (ECGs), Echocardiograms, clinical laboratory evaluations, vital signs assessments, and ophthalmic measurements. The endpoints described in this section will be analyzed according to the analysis methods described in Section

Document: S:\Q_146\Q_03974\MEK-NF-201\Prog_Stat\Documentation\SAP\MEK-NF-201 SAP v1.0.0.docx
Author:

6.12.1. For all applicable safety measures, the baseline value will be defined as the most recent assessment taken on or before the treatment start date, unless otherwise specified.

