AE = adverse event; C = cycle; d = day(s); ECG = electrocardiogram; ePRO = electronic patient reported outcome; ET = early termination; IRT = interactive response technology; MRI = magnetic resonance imaging; NSR-11: 11-point numeric rating scale; PD = pharmacodynamic; PedsQL = Pediatric Quality of Life Inventory; PGIC = patient global impression of change; PGIS = patient global impression of severity; PII = pain interference index; PK = pharmacokinetic; PN = plexiform neurofibroma; P-OMAQ = Pediatric Oral Medicines Acceptability Questionnaire; PRO = patient reported outcome; PROMIS = Patient-Reported Outcomes Measurement Information System; SAE = serious adverse event; SFU = safety follow-up; WOCBP = women of childbearing potential

- 1. Screening visit assessments may occur up to 45 days prior to first dose of study treatment with a minimum Screening period of 7 days to allow for the Baseline PRO assessments to be done 6 days prior to the Baseline visit and for central imaging confirmation of an analyzable target PN. The first 5 participants enrolled in the pediatric cohort must be 9 to 17 years of age at the time of signing informed consent. Enrollment may commence in younger participants (aged 2 to 8 years) after Data Monitoring Committee (DMC) safety review of this run-in cohort (Section 9.5).
- 2. Informed consent/assent process (Section 10.1.3), signing of the informed consent/assent form must be conducted prior to any study procedures being performed. The date the participant signs the ICF will be Day 1 of the Screening period.
- 3. Baseline visit assessments can be performed up to 48 hours prior to first dose of study treatment (defined as Cycle 1 Day 1). For adult participants requiring a tumor biopsy, this assessment may occur during the Screening period, but must be performed after the Screening MRI volumetric assessment has been confirmed evaluable by central radiologic review. All Baseline assessments are to be conducted prior to first dose of study treatment except for the following assessments: post dose 12-Lead ECGs and post dose blood draws for PK sampling.

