- 13. Tumor (core needle) biopsy (Section 8.1.6) This assessment may occur during the Screening period, but must be performed after the Screening MRI volumetric assessment has been confirmed evaluable by central radiologic review and prior to first dose of study treatment. Tumor biopsy will be utilized for PD tumor response in participants ≥ 18 years of age. Participants 2 to 17 years of age should not undergo biopsy unless there is a clinical indication to obtain fresh tumor tissue. If a study biopsy was collected and the participant did not initiate study treatment, this biopsy may be utilized as the baseline biopsy if the participant subsequently re-screens for enrollment.
- 14. Ophthalmic assessments (Section 8.2.7) will include slit lamp with binocular indirect ophthalmoscopy and intraocular pressure measurements. Assessments must be performed by an ophthalmologist. Participants in the pediatric cohort must be evaluated by a pediatric ophthalmologist.
- 15. 12-Lead Electrocardiograms (ECGs) (Section 8.2.4) should be administered in triplicate (approximately 2-3 minutes apart and averaged) and read locally at the Site. Participants should rest in semi-recumbent supine position for at least 5 minutes prior to ECG collection.
 - 15a. At Cycle 1 Day 1, triplicate ECGs are required prior to the first dose of study treatment and approximately 1-hour post dose.
 - **15b.** At Cycle 1 Day 15, triplicate ECGs are required 1-hour post dose of study treatment with a ±10-minute allowed window.
 - 15c. Triplicate ECG may be conducted at any time during the visit after completion of applicable PROs.
- 16. Echocardiogram (Section 8.2.8): Left ventricular ejection fraction (LVEF) will be assessed via echocardiogram.
 - 16a. Echocardiogram required at Screening to confirm or re-confirm Exclusion Criterion 11 and will serve as the Baseline echocardiogram throughout the study.
 - **16b.** Echocardiogram at the ET visit only required if not performed within the past 1 month.
- 17. Strength assessment (Section 8.1.3) will be measured utilizing a dynamometer and Medical Research Council (MRC) Muscle Scale for participants with a target plexiform neurofibroma (PN) that causes motor dysfunction or weakness. The MRC grading assessment should be conducted prior to the dynamometer assessment. Must be done prior to first dose of study treatment at the Baseline visit. Strength assessment at the early termination (ET) visit only required if not performed within the past 1 month.

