Ophthalmic assessments (Section 8.2.7) must be performed by an ophthalmologist throughout the study. Participants in the pediatric cohort must be evaluated by a pediatric ophthalmologist. The Screening ophthalmic exam will reconfirm Exclusion Criterion 12.

For WOCBP, a serum pregnancy test will be conducted at Screening to confirm eligibility (Inclusion Criterion 13).

An echocardiogram (Section 8.2.8) is performed to confirm Exclusion Criterion 11.

Triplicate 12-Lead ECGs (Section 8.2.4) are performed to confirm Exclusion Criterion 9.

A practice 6-minute walk test (Section 8.1.7) must be conducted during Screening, if applicable for the participant.

Baseline and Cycle 1 Day 1

The Baseline visit may occur up to 48 hours prior to first dose of study treatment. However, the PRO assessments will begin 6 days prior to the first day of the Baseline visit. The PII and NRS-11 questionnaires will be completed using the home ePRO device daily for 6 consecutive days prior to the scheduled Baseline visit. At the Baseline visit, the following PRO assessments will be completed prior to all other study assessments to minimize participant bias in the clinic: (PedsQL [paper], PII, NRS-11, PROMIS and PGIS [Table 9]). The paper PedsQL should always be the first PRO administered at the visit.

Because the Baseline visit may occur over 48 hours, Cycle 1 Day 1 will be defined as the date of administration of the first dose of study treatment. The following Baseline assessments are to be conducted prior to the first dose of study treatment:

- PROs (to be completed prior to all other study assessments to minimize participant bias) (Section 8.1.2)
- Concomitant medication and AE/SAE review (Section 8.3);
- Urinalysis / urine pregnancy for WOCBP;
- Blood draw for hematology and serum chemistry (Section 8.2.5);
- Pre-dose PK blood draw (should be within 1 hour prior to dosing when possible) (Section 10.8);
- Vital signs (including height and weight) (Section 8.2.3);
- Pre-dose triplicate 12-Lead ECGs (Section 8.2.4);

- Physical examination and Karnofsky/Lansky performance status (Section 8.2.2)
- Range of motion assessment and strength assessment utilizing a dynamometer and Medical Research Council (MRC) Muscle Scale (for participants with a target PN that causes motor dysfunction or weakness) (Section 8.1.3 and 8.1.5), and should be conducted prior to lab draws if the range of motion or strength assessment may be affected by the lab draw;

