- 6-minute walk test (for participants with a target PN that causes airway or lower extremity motor dysfunction) (Section 8.1.7);
- Target tumor biopsy (if applicable) (Section 8.1.6). For adult participants requiring a
 tumor biopsy, this assessment may occur during the screening period, but must be
 performed after the screening MRI volumetric assessment has been confirmed
 evaluable by central radiologic review and prior to first dose of study treatment. If a
 study biopsy was collected and the participant did not initiate study treatment, this
 biopsy may be utilized as the baseline biopsy if the participant subsequently rescreens for enrollment;
- Bone plate radiograph for participants 2 to 17 years of age (Section 8.2.9); and

Photography of PN (if target PN and/or its effects are visible and amenable to photography) (Section 8.1.4) can be done before or after first dose of study treatment.

After the pre-dose Baseline assessments (as noted above) have been completed and the participant meets all entry criteria (Sections 5.1 and 5.2) they will be assigned study treatment using the IRT and the first dose will be administered at the Site.

The following Baseline assessments are to be conducted after the first dose of study treatment:

- Triplicate 12-Lead ECGs to be conducted approximately 1-hour post-dose;
- PK sampling (Sections 8.5 and 10.8) to be conducted 1- and 2-hours post-dose (± 10-minute allowed window);
- · Record first dose of study treatment in the ePRO device at Site;
- \geq 2-hour observation period following the first dose of study treatment; and
- Concomitant medication and AE/SAE review (Section 8.3).

Participants should be reminded to complete their dosing diary daily and return all study treatment at every visit.

Cycle 1 Day 15

Participants will not take their planned morning dose the day of the study visit. Instead they will take their morning dose of study treatment following the pre-dose PK blood draw in the clinic (Section 10.8).

Additional PK sampling to be conducted at 0.5, 1, 2, 3- and 4-hours post-dose (\pm 10-minute allowed window) (Sections 8.5 and 10.8).

Triplicate 12-Lead ECGs to be conducted 1-hour post-dose (\pm 10-minute allowed window) (Section 8.2.4).

Participants will not be dispensed new study treatment at this visit; therefore, they should continue dosing with the same study treatment that was dispensed at Cycle 1 Day 1.

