4.2.3 Electrocardiogram (ECG) Evaluations

Triplicate 12-lead electrocardiogram (ECG) evaluations are performed at the time points specified in the SoA (Sections 1.3-1.4 of the protocol). At each visit, three ECG assessments are performed in succession, approximately 3 minutes apart, these triplicate recordings are averaged to give the result for a given visit and parameter. In the case that not all ECG assessments were recorded, the average of the recording(s) taken will be used. At the C1D1 visit measurements are taken both pre-dose and post-dose.

Table 9 presents the quantitative and qualitative ECG parameters that were collected.

Table 9: ECG Parameters

ECG Parameters (Unit)
Conduction Times
Heart rate (bpm)
RR Interval (msec)
PR Interval (msec)

Document: S:\Q_146\Q_03974\MEK-NF-201\Prog_Stat\Documentation\SAP\MEK-NF-201 SAP v1.0.0.docx

Author:

QRS Interval (msec)
QT Interval (msec)
QTc Interval (msec)
QTcF Interval (msec)

For the quantitative ECG parameters, the change from baseline value at each post-baseline visit will be calculated as the difference between the measurement obtained at the specific post-baseline visit and the baseline value.

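### The SAP's date-only safety baseline, read literally, makes the ECG taken about 1 hour after the first dose the QTcF baseline, and no ECG-specific rule says otherwise

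*SAP*

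**What the plan says.** The general rule in SAP 4.2 is that "the baseline value will be defined as the most recent assessment taken on or before the treatment start date, unless otherwise specified". It leaves room for exceptions.

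The ECG schedule puts two sets of recordings around the first dose. Protocol 1.3, footnote 15a, reads: "At Cycle 1 Day 1, triplicate ECGs are required prior to the first dose of study treatment and approximately 1-hour post dose". Protocol Table 7 defines Cycle 1 Day 1 as the day on which the first dose is given. It lists the post-dose set ("Triplicate 12-Lead ECGs to be conducted approximately 1-hour post-dose") among the Baseline assessments done after dosing. Footnote 3 of Protocol 1.3 requires Baseline assessments before the first dose, "except for the following assessments: post dose 12-Lead ECGs and post dose blood draws for PK sampling".

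SAP 4.2.3 recognises both sets ("At the C1D1 visit measurements are taken both pre-dose and post-dose") but does not say which one is baseline. SAP 6.12.1.3 then summarises QTcF change from baseline by post-baseline visit, in the categories <30, 30 to 60 and >60 msec. It does not define an ECG baseline either.

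**The concern.** A baseline should describe the participant before exposure. Most safety measures at the Baseline visit are taken before dosing, so a date rule does no harm there. The ECG is the exception: the protocol deliberately adds a recording after the first dose on the same date. A date-only rule cannot separate the two sets, and a rule that takes the latest reading prefers the wrong one.

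Two things are at stake. First, ECG change is part of a secondary safety endpoint (Protocol Table 1), and the QTcF change tables depend on which triplicate is subtracted. Second, if the post-dose triplicate is the baseline, the only ECG taken after the very first dose is no longer reported as an on-treatment observation. Two programmers could each follow the SAP and produce different QTcF change tables.

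**Working it through.** The plan states no figure to reproduce, so the check applies the written rule to the scheduled ECGs.

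**Step 1: candidates.** Three scheduled ECG sets can fall on or before the treatment start date:

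- Screening.
- Cycle 1 Day 1 pre-dose (Protocol 1.3 footnote 15a; Table 7).
- Cycle 1 Day 1, about 1 hour post-dose (same sources). It falls on the treatment start date because Cycle 1 Day 1 is defined as the date of first dose.

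**Step 2: apply SAP 4.2.** If clock times are used to order the sets, the latest is the post-dose triplicate. If only dates are used, the two Cycle 1 Day 1 sets tie when both are done that day.

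**Step 3: look for an exception or tie-break.**

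- SAP 4.2.3 mentions both sets and assigns neither.
- SAP 6.12.1.3 has no definition.
- SAP 4.2.2 does have a rule for several assessments at one visit, but it covers laboratory data and ranks scheduled over unscheduled. Both ECG sets are scheduled.
- SAP 5.6 works in study days, not clock time.

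Elsewhere the SAP is specific when it needs to be. SAP 4.1.3.10 names the Screening scan as the tumour-volume baseline, and SAP 4.2.1.1 ties treatment-emergent events to the taking of the first dose. There is no equivalent for ECGs.

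**Step 4: effect on reported change.** Let P be the pre-dose QTcF, d the acute effect at 1 hour, and V the value at a later visit. The post-dose baseline is P + d, so

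reported change = V − (P + d) = (V − P) − d.

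In terms of change from the pre-dose value, the category limits become 30 + d and 60 + d msec. The documents give no value for d. The range −10 to +10 msec below is an assumption made only to show scale.

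| d (msec, assumed) | Effective limits (msec) | A true change of 65 is reported as |
|---|---|---|
| −10 | 20 and 50 | 75 |
| 0 | 30 and 60 | 65 |
| +10 | 40 and 70 | 55 |

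**Step 5: effect on category shares.** Assume further that changes from the pre-dose value at a visit are normal with mean 0 and SD 15 or 20 msec. The share at or above 30 msec is P(Z ≥ (30 + d)/SD).

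| SD (assumed) | d = 0 | d = +10 | d = −10 |
|---|---|---|---|
| 15 | 2.3% | 0.4% | 9.1% |
| 20 | 6.7% | 2.3% | 15.9% |

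For the >60 msec category the formula is P(Z > (60 + d)/SD). With SD 15 the share goes from about 0.003% (d = 0) to 0.04% (d = −10); with SD 20 it goes from 0.13% to 0.62%. The larger difference is 0.62 − 0.13 = 0.49 percentage points, about half a participant per 100 at a visit. On these assumptions the 30 msec boundary is sensitive and the 60 msec boundary barely moves.

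**Step 6: post-baseline coverage.** Excluding early termination and safety follow-up, the Treatment Phase has 9 scheduled ECG time points after the first dose: Cycle 1 Day 1 post-dose, Cycle 1 Day 15, Cycle 2 Day 15, Cycles 5, 9, 13, 17 and 21, and Cycle 24. Eight have a clear post-baseline place. The ninth, Cycle 1 Day 1 post-dose, becomes baseline under the literal rule. Even with a pre-dose baseline its place is not stated, because SAP Table 3 labels Cycle 1 Day 1 as the Baseline visit while SAP 6.12.1.3 reports by post-baseline visit.

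**The case against.** The strongest reply is that a pre-dose baseline is plainly intended. Footnote 3 of Protocol 1.3 treats the post-dose ECG as an exception to the pre-dose requirement. Protocol 7.1.2 speaks of QTcF changes from Baseline found after the first dose, which presupposes a baseline that precedes dosing. SAP 4.3.4 describes baseline characteristics as those present before first administration. This stands as evidence of intent, and a careful programmer may well do the right thing. It is not a rule: none of these passages says which ECG triplicate is the baseline, and the one rule that is written points the other way.

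The reply on consequence also stands. The summaries carry no hypothesis test or decision rule. Absolute QTcF categories at later visits do not use the baseline. Cycle 1 Day 15 also has a triplicate 1 hour after dosing (footnote 15b), so post-dose QTcF on repeated dosing is still reported.

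Three stronger readings are tempting, and the documents do not support them:

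- **That both Cycle 1 Day 1 sets are averaged into one baseline.** SAP 4.2.3 says "these triplicate recordings are averaged to give the result for a given visit and parameter", but the same sentence describes three recordings about 3 minutes apart, and the section then separates pre-dose from post-dose. Six recordings on either side of a dose are not one triplicate. The averaging of repeated records in SAP 5.6 is written for efficacy assessments.
- **That the rule hides QT prolongation.** This needs d to be positive. The documents give no sign, and a negative d would overstate changes.
- **That the pre-dose ECG will often fall on an earlier day, leaving the post-dose set alone on the start date.** Footnote 3 does say "Baseline visit assessments can be performed up to 48 hours prior to first dose of study treatment", so this is possible. But footnote 15a places the pre-dose triplicate at Cycle 1 Day 1, which points to a same-day recording.

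**Conclusion.** The point holds as a minor defect. SAP 4.2 contains a stated rule that, followed as written, selects an on-drug ECG as the QTcF baseline, or leaves an unresolved tie if only dates are compared. No other passage overrides it for ECGs.

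Under the literal reading, every QTcF change is displaced by exactly the acute 1-hour effect. That effect has unknown size and sign and may be zero, so no bias can be quantified from the documents; the shares shown above rest wholly on assumed values of d and SD. The first-dose post-dose ECG is also lost as a post-baseline observation. The consequence is confined to how ECG change is reported. It does not touch the efficacy analyses, the definition of treatment-emergent events, or the absolute QTcF categories at later visits.

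**What to change.** Make two short additions to the SAP:

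- **SAP 4.2.3:** state that the ECG baseline is the mean of the last triplicate obtained before the first dose, that is, the Cycle 1 Day 1 pre-dose set, or Screening if that set is missing.
- **SAP 6.12.1.3:** report the Cycle 1 Day 1 post-dose triplicate as a separate post-baseline time point.

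The general rule in SAP 4.2 can stay, since it already allows exceptions and this would be one. The cost is about two sentences and the matching programming. No new data are needed, because the pre-dose and post-dose triplicates are already separate scheduled assessments.

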4.2.1 Adverse Events

An adverse event (AE) is any untoward medical occurrence in a patient or clinical study participant, temporally associated with the use of study treatment, whether or not considered related to the study treatment.

An AE can therefore be any unfavorable and unintended sign (including an abnormal laboratory finding), symptom, or disease (new or exacerbated) temporally associated with the use of study treatment.

AE data is collected from the time of informed consent/assent to 30 days after the last dose of study treatment at the timepoints specified in the SoA (Sections 1.3-1.4 of the protocol). Missing AE data will be handled according to the rules specified in Section 5.5.2.1.

4.2.1.1 Adverse Event Definitions

Certain AEs are specified as adverse events of special interest (AESI). AESIs for this study were marked by the investigators and will be reported as such. AESIs include but are not limited to the following cases in Table 8.

Table 8: Adverse Events of Special Interest

Gastrointestinal (reported as AESI if Grade ≥3)		
Diarrhea	Nausea	Vomiting
Eye Disorders (reported as A		
Retinal Vein Occlusion (RVO)		Optic neuropathy
Retinopathy	Retinal detachment	
Cardiac Disorders (reported as AESI if Grade ≥2)		
Ejection fraction decreased		Left ventricular dysfunction
Neurological Disorders (reported as AESI if Grade ≥2)		
Confusion	Hallucinations	Delirium
Infections and Infestations (r	eported as AESI if Grade ≥3)	
Viral Rash		
Skin Disorders (reported as AESI if Grade ≥3)		
Rash*	Acneiform Rash*	

^{*}Rash and Acneiform Rash were considered an AESI for Grade ≥2 in earlier versions of the protocol. Due to this, there may be some Grade 2 rashes marked as AESIs by the investigators, which will be reported as such.

The AESI of "Rash" is a composite term, all PTs which will be considered as a "Rash" AESI are listed in Appendix 2.

AEs will be summarized combined across the Treatment and LTFU phases. A TEAE is defined as an AE that starts or worsens on or after the first dose of study treatment is taken, including those occurring or increasing in severity up to 30 days after the last dose of study treatment.

A treatment-emergent serious adverse event (SAE) is defined as a TEAE that, at any dose; results in death; is life-threatening; requires inpatient hospitalization or prolongation of existing hospitalization; results in persistent disability/incapacity; is a congenital anomaly/birth defect; or is assessed by the investigator as an otherwise important serious medical event.

Document: S:\Q_146\Q_03974\MEK-NF-201\Prog_Stat\Documentation\SAP\MEK-NF-201	SAP
v1.0.0.docx	
Author	

An AE will be classified as a study treatment-related AE if it has an investigator determination of related to study treatment. Investigators will provide their assessment as related to study treatment, not related to study treatment, or not applicable. AEs that are missing a treatment related/unrelated classification will not be imputed and "missing" will be presented as a category in summary tables.

An AE will be classified as a study procedure-related adverse event if it has an investigator determination of related to study procedure. Investigators will provide their assessment as related to study procedure, not related to study procedure, or not applicable. AEs that are missing a study procedure related/unrelated classification will not be imputed and "missing" will be presented as a category in summary tables.

Additionally, the following terms are defined:

- Adverse reaction (AR) any noxious and unintended response to a medical product or procedure, for which a causal relationship with the product or procedure is at least a reasonable possibility (i.e., the relationship cannot be ruled out).
- Serious adverse reaction (SAR) an SAE for which a causal relationship with the product or procedure is at least a reasonable possibility (i.e., the relationship cannot be ruled out).
- Suspected unexpected serious adverse reaction (SUSAR) an SAR that is judged as unexpected. An event is considered "unexpected" if it is not listed as expected in the reference safety information (RSI) section of the investigator brochure (IB) or summary of product characteristics.

The intensity of all AEs will be graded according to the NCI Common Terminology Criteria for Adverse Events (CTCAE) Version 5.0. For AEs not listed in the CTCAE, the following grading system should be used:

- CTCAE Grade 1 Mild; asymptomatic or mild symptoms; clinical or diagnostic observations only; treatment not indicated.
- CTCAE Grade 2 Moderate; minimal, local, or noninvasive treatment indicated; limiting age-appropriate instrumental activities of daily living (ADL)*.
- CTCAE Grade 3 Severe or medically significant but not immediately life-threatening; hospitalization or prolongation of hospitalization indicated; disabling; limiting self-care ADL**.
- CTCAE Grade 4 Life-threatening consequences; urgent treatment indicated.
- CTCAE Grade 5 Death related to AE.

*Instrumental ADL refer to preparing meals, shopping for groceries or clothes, using the telephone, managing money, etc.

**Self-care ADL refer to bathing, dressing and undressing, feeding self, using the toilet, taking medications, and not bedridden

An AE leading to study discontinuation will be defined as an AE where the primary reason for discontinuation of study (on the 'End of Study' CRF page) was recorded as being an AE.

An AE leading to treatment discontinuation will be defined as an AE where the action taken with study treatment was recorded as 'Study treatment withdrawn' on the 'Adverse Events' CRF page.

Document: S:\Q_146\Q_03974\MEK-NF-201\Prog_Stat\Documentation\SAP\MEK-NF-201 SAP v1.0.0.docx

Author:

SpringWorks Therapeutics Protocol Number: MEK-NF-201

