8.3.1. Adverse Events of Special Interest

Table 10 Adverse Events of Special Interest (AESI)

Gastrointestinal (reported as AESI if Grade ≥ 3)			
Diarrhea	Nausea Vomiting		
Eye Disorders (reported as AESI if Grade ≥ 2)			
Retinal Vein Occlusion (RVO)	Uveitis Optic neuropathy		
Retinopathy	Retinal detachment		
Cardiac Disorders (reported as AESI if Grade ≥ 2)			
Ejection fraction decreased	Cardiac failure Left ventricular dysfunction		
Neurologic Disorders (reported as AESI if Grade ≥ 2)			
Confusion	Hallucinations Delirium		
Skin Disorders (reported as AESI if Grade ≥ 3)			
Rash	Acneiform rash		

These are selected, non-serious AEs and SAEs that **must be reported within 24 hours** regardless of relationship to study treatment. For participants who experience signs or symptoms that may be consistent with an AESI, sites are strongly encouraged to immediately notify the Medical Monitor of the event via email and/or phone. Documentation of potential AESIs should occur after discussion between the investigator and the Medical Monitor. Many of these events may also qualify as SAEs. Any event that meets the criteria described in Table 10 must be reported regardless of investigator-determined relationship to study treatment (unless otherwise

specified). Investigators/study coordinators/designated site personnel are required to record these experiences in the eCRF (as described in the eCRF completion guidance document) and to provide supplemental information (such as medical history, concomitant medications, investigations, etc.) about the event. Please note this table lists known AESI, and additional events may be identified during the course of the study.

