6.12.1.1 Adverse Events

Only TEAEs will be presented in summary tables, as defined in Section 4.2.2.1. An overview of these TEAEs will be presented by age cohort summarizing the number and percentages of participants with TEAEs; SAEs; TEAEs of at least Grade 3 severity; study-drug related AEs; and AEs leading to dose modification, interruption, reduction, and discontinuation. The number and percentage of participants with a maximum recorded toxicity Grade 1-5 will also be presented.

Separate summaries by SOC and PT will be provided for the incidence of TEAEs (also for TEAEs by PT only), incidence of TEAEs by highest severity, incidence of SAEs, TEAEs of at least Grade 3 severity, study drug-related TEAEs, study drug related SAEs, study drug-related TEAEs of at least Grade 3 severity, study procedure related TEAEs, TEAEs leading to discontinuation, most common TEAEs related to study drug (occurring in ≥5% of overall cohort), TEAEs leading to dose reduction, TEAEs leading to dose interruption and AESIs – all as defined in Section 4.2.2.1. In addition, a summary of TEAEs by PT only will also be presented. All summaries will present absolute participant counts (n) and TEAE event counts. Percentages (%) will be calculated based on the number of participants at risk. Additionally, TEAEs will be summarized by cycle of first onset (After Cycle 6, cycles will be grouped either as Cycles 7-12, or Cycle 13 and later).

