Appendix 2 Rash Composite Term PT List

The following PTs will be considered as a Rash AESI event:

- Dermatitis
- Dermatitis acneiform
- Dermatitis exfoliative
- Dematitis exfoliative generalized
- Rash
- Rash maculopapular
- Rash erythematous
- Rash macular
- Rash popular
- Rash pustular
- Rash pruritic
- Exfoliative rash
- Papule
- Skin exfoliation
- Rash maculovesicular
- Rash morbilliform
- Rash papulosquamous
- Rash vesicular
- Eyelid rash
- Nodular rash

Document: S:\Q_146\Q_03974\MEK-NF-201\Prog_Stat\Documentation\SAP\MEK-NF-201 SAP v1.0.0.docx

Author:

MEK-NF-201 SAP v1.0.0

Final Audit Report 2023-11-03

Created: 2023-11-03 (Greenwich Mean Time)

Ву:

Status: Signed

Transaction ID: CBJCHBCAABAA7hJCHnYK4rze2T3XvqmYUoRwSSfE133n

Number of Documents: 1

Document page count: 61

Number of supporting files: 0

Supporting files page count: 0

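### The rash AESI rate mixes two grade thresholds because investigator marks made under the earlier Grade 2 rule are kept, and no composite rash rate at a single grade is planned

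*SAP*

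**What the plan says.** Four places bear on how a rash AESI is counted.

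- **Source of the classification.** SAP 4.2.1.1: "AESIs for this study were marked by the investigators and will be reported as such".
- **Threshold.** Protocol 8.3.1, Table 10 (Amendment 4) has "Skin Disorders (reported as AESI if Grade ≥ 3"), and SAP Table 8 agrees: "Skin Disorders (reported as AESI if Grade ≥3"). The SAP footnote adds that "Rash and Acneiform Rash were considered an AESI for Grade ≥2 in earlier versions of the protocol", and continues: "Due to this, there may be some Grade 2 rashes marked as AESIs by the investigators, which will be reported as such". Grade 2 rashes marked for this reason thus stay in the AESI count.
- **Composite.** SAP 4.2.1.1 calls rash a composite term and points to Appendix 2, which lists 20 preferred terms under the sentence "The following PTs will be considered as a Rash AESI event". The appendix gives no grade.
- **Tables.** SAP 6.12.1.1 plans summaries by system organ class and preferred term that include "TEAEs leading to dose reduction, TEAEs leading to dose interruption and AESIs". The same paragraph plans "incidence of TEAEs by highest severity, incidence of SAEs, TEAEs of at least Grade 3 severity". It plans no split of AESIs by protocol version and no AESI analysis at a common grade.

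**The concern.** An incidence is interpretable when the same event counts in the same way for everyone. Here the event is defined by a mark whose rule changed during the trial. A Grade 2 rash recorded under an earlier version could be marked and enters the AESI table. An identical rash recorded under the current version should not be marked and stays out. The resulting percentage estimates neither the Grade 2 rate nor the Grade 3 rate.

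This matters because rash is an expected effect of the drug. Protocol 2.3 lists it among the most frequently reported events in patients with advanced cancer, where most events were mild to moderate. Protocol 1.1 names acneiform rash as the most common event leading to dose reduction in the earlier plexiform neurofibroma study. If many rashes fall below Grade 3, the choice of threshold largely determines the number that a reader takes away as the rash AESI incidence.

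**Working it through.** The documents state no rash AESI rate, so there is no figure of the plan to reproduce. The check compares the definitions and then shows how the reported rate depends on the mixture.

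**1. Which rule applies to a Grade 2 rash**

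| Source | Is a Grade 2 rash an AESI? |
|---|---|
| Earlier protocol versions (SAP Table 8 footnote) | Yes |
| Protocol Table 10, Amendment 4 | No |
| SAP Table 8 | No |
| SAP 4.2.1.1 reporting rule | Yes, if the investigator marked it |

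Participants are treated for up to 24 cycles and may continue into long-term follow-up, so one person can pass through several protocol versions. The version that matters is the one in force when the rash was recorded, not the one at enrolment.

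**2. Reported rate under the mixture**

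Let p3 be the share of participants with a Grade 3 or higher rash and p2 the share whose worst rash is Grade 2. Let f be the share of the p2 group with a Grade 2 rash marked as an AESI under the earlier threshold. If every Grade 3 or higher rash was marked:

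reported rate = p3 + f × p2

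A uniform Grade 3 rule gives p3, and a uniform Grade 2 rule gives p3 + p2. Since f × p2 cannot be negative, the reported rate is never below p3.

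None of the three inputs is in the documents. With assumed p3 = 6%, p2 = 20% and the planned cohort size of 50:

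| f | Reported rate | Expected count of 50 |
|---|---|---|
| 0 | 6% + 0 = 6% | 3 |
| 0.25 | 6% + 5% = 11% | 5.5 |
| 0.5 | 6% + 10% = 16% | 8 |
| 0.75 | 6% + 15% = 21% | 10.5 |
| 1 | 6% + 20% = 26% | 13 |

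The underlying rashes are the same in every row. Over p3 from 2% to 10% and p2 from 10% to 30%, moving f from 0 to 1 adds p2, that is 10 to 30 percentage points.

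**3. Whether the other planned tables recover the rate**

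The Grade 3 and highest-severity tables use the CTCAE grade and do not depend on the mark, so each rash term can be read there at one threshold. They do not give the composite. A participant can have several of the 20 listed terms, so the participant-level count lies somewhere between the largest single row and the sum of the rows. For example, two terms with 3 of 50 each (assumed) are compatible with anything from 3 participants (6%) to 6 participants (12%).

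**The case against.** The strongest reply has five parts.

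- **Disclosure and grade-based tables.** The SAP states the issue in a footnote and already plans grade-based tables by preferred term. This stands as partial mitigation. What remains missing is one de-duplicated composite row per grade.
- **Status of the mark.** Under Protocol 8.3.1 an AESI is a 24-hour reporting category, and potential AESIs are documented after discussion with the Medical Monitor. Reporting events as they were handled at the time is defensible, and moving the marks to a listing would drop them from the summary. This stands, so the marked summary should be kept.
- **Reach.** A reader might infer that comparisons between formulations are distorted. They are not: SAP 6.12.1.7 mirrors the summary of all TEAEs, and no AESI table by formulation is planned. A reader might also infer a distorted contrast between cohorts. SAP 2.2 pauses paediatric enrolment after five participants while adults enrol continuously, so uneven exposure to the versions is possible. Without the date of the threshold change or enrolment dates, it is not shown.
- **Appendix 2 as a rival definition.** Read literally, its opening sentence makes a rash of any grade an AESI. The more natural reading, given 4.2.1.1, is that the mark selects events and the list groups them. The wording needs a clarification but does not establish two competing derivations.
- **Size.** The rates in the illustration are assumed. SAP 1.1 reports that the two rashes leading to dose reduction in the earlier study were Grade 1, and the footnote says only that there may be some Grade 2 marks. A claim of large inflation is not supported.

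**Conclusion.** The point holds in a limited form. As planned, the rash AESI rate combines two thresholds, and the plan contains no participant-level composite rash rate at either one. The direction is known on one assumption, that all Grade 3 or higher rashes were marked: the reported rate equals or exceeds the uniform Grade 3 rate. The size cannot be derived, because the documents give neither the date of the change, nor the number of rashes recorded under each version, nor the grade distribution. The 6% to 26% range illustrates sensitivity and is not an estimate.

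Severity is minor. AESI incidence carries no hypothesis, the issue is disclosed, and it touches one descriptive safety table. The all-TEAE, Grade 3 and formulation tables are unaffected.

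**What to change.** 1. Keep the investigator-marked AESI summary and its footnote.
2. Add composite rash rows to the AESI table, by cohort, derived for all participants from the Appendix 2 preferred terms and the recorded CTCAE grade. Count each participant once per row. Show Grade 3 or higher as the current definition and Grade 2 or higher as supporting.
3. Use the Grade 3 row for any statement of rash AESI incidence.
4. State in SAP 4.2.1.1 or Appendix 2 that the list groups terms and does not by itself make a rash of any grade an AESI. Because Dermatitis acneiform is on the list while Table 8 shows acneiform rash as its own entry, say whether it is reported within the composite, separately, or both.
5. Correct the cross-reference in SAP 6.12.1.1. It cites Section 4.2.2.1 (Hematology) for definitions that stand in 4.2.1.1.

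The cost is one extra derivation from coded terms and grades already collected, with no change to trial conduct. The derived counts may differ from the investigator marks, and a sentence under the table should explain why.
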